7.3 Subject Population(s) for Analysis

Our primary analysis will be an intention to treat analysis. The data for all participants randomized into the study, regardless of study group, will be subjected to the study analyses, both for the primary and any applicable secondary analyses.

8 Safety and Adverse Events

Both the IRB and participants will be notified immediately of any new information in regard to this pilot study that affects participants' participation in the study. Unexpected and serious adverse events that occur will be reported to the IRB according to the IRB protocol. The primary investigator (PI) and research investigator(s) involved will monitor a review of the outcome, anticipated effects, and adverse event data in determining whether the study should continue, change, or terminate. If there is a major unresolved dispute between a research investigator and a research participant or between research investigators, a letter will be submitted to the IRB describing the dispute and identifying the parties involved.

8.1 Definitions

Unanticipated Problems Involving Risk to Subjects or Others

Any incident, experience, or outcome that meets all of the following criteria.

- Unexpected in nature, severity, or frequency (i.e., not described in study-related documents such as the IRB-approved protocol or consent form, etc.)

CONFIDENTIAL

This material is the property of the NYU School of Medicine and Langone Medical Center. Do not disclose or use except as authorized in writing by the study sponsor

- Related or possibly related to participation in the research (i.e., possibly related means there is a reasonable possibility that the incident experience, or outcome may have been caused by the procedures involved in the research)
- Suggests that the research places participants or others at greater risk of harm (including physical, psychological, economic, or social harm)

Unanticipated Adverse Device Effect

An unanticipated device effect is any serious adverse effect on health or safety, or any life-threatening problem or death caused by, or associated with a device, if that effect, problem, or death was not previously identified in nature, severity, or degree of incidence in the investigational plan or application (including a supplementary plan or application), or any other unanticipated serious problem associated with a device that relates to the rights, safety, or welfare of participants.

Serious injury

Any injury or illness that is any one of the following:

- life-threatening
- results in permanent impairment of a body function or permanent damage to body structure
- necessitates medical or surgical intervention to preclude permanent impairment of a body function or permanent damage to a body structure

Adverse Event

An **adverse event** (AE) is any symptom, sign, illness or experience that develops or worsens in severity during the course of the study. Intercurrent illnesses or injuries will be regarded as adverse events.

Abnormal results of diagnostic procedures are considered adverse events if the abnormality:

- results in study withdrawal,
- is associated with a serious adverse device effect,
- is associated with clinical signs or symptoms,
- leads to additional treatment or to further diagnostic tests, or
- is considered by the investigator to be of clinical significance.

Based on International and U.S. guidelines on serious adverse events from medical devices (including the Office of Human Research and Protection of the U.S. Department of Health and Human Services; FDA regulations at 21 CFR §312.32[a]; 1996 International Conference on Harmonization E-6 Guidelines for Good Clinical Practice; ISO/DIS 14155-Clinical investigations of medical devices in humans, Good Clinical Practices, 2008), we classify a severe adverse event related to rtACS as a documented event that:

- 1) Based on scientific judgment is determined to be caused or aggravated by the application of current to the head, such that serious adverse events not linked to stimulation are excluded, even if they are subject to reporting requirements, AND
- 2) Results in irreversible damage of brain tissue, OR
- 3) Results in persistent disability or incapacity that produces an unwanted and substantial disruption of a person's ability to conduct normal life functions (i.e., the adverse effect resulted in an unwanted significant, persistent or permanent change, impairment, damage or disruption in the participant's body function/structure, physical activities and/or QoL), OR
- 4) Results in unexpected inpatient hospitalization or prolongation of existing hospitalization, where emergency room visits that do not result in admission to the hospital should be evaluated for one of the other serious outcomes (e.g., life-threatening; required intervention to prevent permanent impairment or damage; other serious medically important event), OR
- 5) Results in death or is life-threatening where the patient was at substantial risk of dying as a result of the adverse event, or use of the device was discontinued based on evidence rtACS might have resulted in death, OR

CONFIDENTIAL

This material is the property of the NYU School of Medicine and Langone Medical Center. Do not disclose or use except as authorized in writing by the study sponsor

6) Medical or surgical interventions were necessary to preclude permanent imminent impairment of a body function due to rtACS, or prevent permanent damage to a body structure, due to rtACS.

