5.2 Treatment Regimen

After obtaining written informed consent, participants will be allocated (1:1 ratio) to either rtACS or sham stimulation intervention group. The intervention protocol for each group involves 10 daily sessions delivered over 2 weeks, 1 session per day, < 60 minutes of continuous/sham stimulation (0-100 Hz) per day following the established dose parameters. The rtACS group will receive the stimulation dose per protocol. During a sham stimulation session, the DC-Stimulator MC will be programmed accordingly which may include brief periods of stimulation at the beginning and/or end of the session, serving to

CONFIDENTIAL

This material is the property of the NYU School of Medicine and Langone Medical Center. Do not disclose or use except as authorized in writing by the study sponsor

mimic the effects of a true stimulation session. Researchers report this is necessary to designing the masking component of this study.

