5.8.2 Storage

The devices and supplies will be located in a treatment room designated for research purposes at NYU Langone Eye Center. The backup device will be appropriately placed for storage in a locked room.

6 Study Procedures

Screening procedures will be conducted in a research-designated room at the Centers appropriate for the setup and confidentiality for the interview procedures. Baseline assessments, intervention sessions, post-intervention and follow-up assessments for all participants will be conducted in a research-designated room at NYU Langone Eye Center.

Per standardized assessment guidelines and in order to accommodate and minimize the amount of time subjects may be willing and/or able to participate in research procedures at the Eye Center, assessments of functional ability and QoL may be coordinated with subjects for virtual administration (e.g., via phone, Webex, etc.).

The IRB-approved recruitment script used during the screening procedures for this study will be used for contacting new patients, in conjunction with the COVID-19 Updates Research Participant Recruitment script provided by the OSR/IRB. In addition, the applicable COVID information sheet for potential and enrolled subjects will be provided in the appropriate situation and while they are applicable to subjects.

Trained personnel who are not involved in data collection or analysis will be involved in the programming of the DC-Stimulator MC according to group allocation for each participant and the masking procedures that distinguish the delivery of rtACS versus sham stimulation. All intervention procedures will be conducted the same for both groups (rtACS and sham). Adverse events/adverse effects will be assessed in either condition.

Refer to Attachment 5 for the study schedule of events and Attachment 6 for documentation forms described below.

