8.2 Recording of Adverse Device Effects

Prior to and at each contact with the participant, the investigator will evaluate adverse device effects by examination and, as appropriate, by specific questioning. Information on all adverse device effects will be recorded immediately in the source document and in the appropriate adverse effect module of the Research Activities Checklist (see Attachment 7) and Case Report Form. All clearly related signs, symptoms, and abnormal diagnostic procedure results will be recorded in the source document, grouped under one diagnosis.

All adverse device effects occurring during the study period will be recorded. The clinical course of each event will be followed until resolution, stabilization, or until it has been determined that the study treatment or participation is not the cause. Serious adverse device effects that are still ongoing at the end of the study period will be followed up to determine the final outcome (see section 8.3).

The minimum initial information to be captured in the participant's source document concerning the adverse device effect includes:

- Study identifier
- Study Center
- Subject number
- Device model and serial number
- A description of the event
- Date of onset
- Investigator assessment of the association between the event and study treatment
- Current status
- Whether study treatment was discontinued
- Whether the event is serious and reason for classification as serious

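### No all-cause count of serious adverse events by arm is secured: the one classification covering hospitalisation, disability and death requires a causal judgement, and the section 8.2 recording rule covers device effects only

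*Combined protocol and SAP*

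**What the plan says.** - **The classification (8.1).** The passage opens "we classify a severe adverse event related to rtACS as a documented event that" and then lists six numbered criteria. Criterion 1 reads "Based on scientific judgment is determined to be caused or aggravated by the application of current to the head", and continues "such that serious adverse events not linked to stimulation are excluded, even if they are subject to reporting requirements". Criteria 2 to 6 are outcomes: brain damage, lasting disability, hospitalisation, death or threat to life, and intervention to prevent permanent harm. Part of criterion 5, and criterion 6, carry their own wording about rtACS as the cause.
- **Adverse event (8.1).** An adverse event "is any symptom, sign, illness or experience that develops or worsens in severity during the course of the study". There is no causal test, and intercurrent illness counts.
- **Serious injury (8.1).** This is defined by outcome alone, but it lists neither hospitalisation nor death.
- **Recording (8.2).** The rule and its minimum data list are for adverse device effects. The list has separate items for "Investigator assessment of the association between the event and study treatment" and "Whether the event is serious and reason for classification as serious".
- **Both arms.** Section 6 (Study Procedures, introductory text) says "Adverse events/adverse effects will be assessed in either condition". Under 5.2, a sham session is programmed in a way "which may include brief periods of stimulation at the beginning and/or end of the session".
- **Masking.** Sections 3.1 and 5.7 mask participants and interventionist. Section 8.5 withholds allocation until all participants finish, but provides for earlier unmasking to manage an adverse event.

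**The concern.** Whether an event is serious is a matter of outcome. Whether the device caused it is a matter of opinion, and in a sham-controlled trial the randomised comparison is the better evidence on that question. When the only full list of serious outcomes admits an event after a causal opinion, and the recording rule is also limited to device effects, a hospitalisation judged unlinked has no assured place in the data.

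Three uses are at stake. Section 8 has the investigators use adverse event data to decide whether the study continues, changes or stops. Section 10.1 has no predetermined stopping rules, so that decision depends on what those data contain. And the pilot is meant to inform a larger sham-controlled trial, which needs to know the background rate of serious events as well as those attributed to current.

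**Working it through.** There is no figure in the plan to reproduce: section 7.1 gives 16 participants without an assumed event rate. The check is mainly a reading of the rules side by side.

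**1. Is there another route to an all-cause serious-event record?**
- The adverse event definition in 8.1 is all-cause but does not grade seriousness.
- No recording or reporting rule in section 8 uses the serious injury definition.
- The detailed IRB reporting in 8.3 is for unexpected and related problems and unanticipated device effects. Section 8.4 covers known effects of the intervention and of study procedures.
- The opening of section 8 has unexpected and serious events reported to the IRB, with no causal condition in that sentence, but it does not define serious.
- Sections 8.6 and 10.1 have adverse events reviewed, without a seriousness rule or a tabulation by arm.

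So the text assesses and reviews events of all causes but does not secure a serious-event count from them.

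**2. Does criterion 1 govern the whole list?** The criteria are joined by one AND and then ORs, without brackets.
- Reading A: 1 AND (2 OR 3 OR 4 OR 5 OR 6). Every serious outcome must be attributed to current.
- Reading B: (1 AND 2) OR 3 OR 4 OR 5 OR 6. Attribution binds only brain damage, and a hospitalisation of any cause would qualify.

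The exclusion wording in criterion 1 favours reading A. The passage also moves between *severe* and *serious*, so two sites could classify the same event differently.

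**3. What does the filter do in each arm?** The documents do not say who makes the judgement in criterion 1, or when. For illustration:
- about 16 / 2 = 8 participants per arm (7.1, 1:1 allocation);
- an **assumed** all-cause risk p per participant of 5%, 10% or 20%, equal in both arms;
- an **assumed** 30% of events attributed to current.

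Expected events per arm are 8p. The chance of at least one event in 16 participants is 1 − (1 − p)^16. Under masked attribution at the same rate in both arms, 0.3 × 8p events per arm are classified.

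| p | Expected per arm | P(at least one in 16) | Classified per arm, masked | Left out per arm, masked | Classified in sham if allocation is known and none is attributed |
|---|---|---|---|---|---|
| 5% | 0.4 | 0.56 | 0.12 | 0.28 | 0 |
| 10% | 0.8 | 0.81 | 0.24 | 0.56 | 0 |
| 20% | 1.6 | 0.97 | 0.48 | 1.12 | 0 |

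Masked judgement thins both arms alike. Only knowledge of allocation empties the sham arm selectively.

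**4. How much could a formal comparison show anyway?** Fisher's exact test, two-sided, 8 against 8: 4/8 v 0/8 gives p = 0.077, and 5/8 v 0/8 gives p = 0.026. A test would be weak under any definition.

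**The case against.** The strongest reply is that the clause does not define seriousness at all. It defines a category of events related to rtACS, and such a category is bound to contain a relatedness test. Criterion 1 itself acknowledges other serious events, some of them reportable. **This stands as far as it goes**: a reader might infer that the plan makes causation part of seriousness in general, and the text does not say that. It does not close the gap, because no causation-free definition of a serious adverse event appears elsewhere.

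A reader might also infer that nearly all serious events in the sham arm drop out by construction. **The documents do not support this.** Under the default in 8.5 allocation is unknown, so an assessor cannot discount sham events selectively, and sham may include brief stimulation. The asymmetry needs known allocation. Section 8.5 allows that when an adverse event is being managed, but does not make it the rule.

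A third inference, that the arms cannot be compared on safety, **is also too strong**. Events are assessed in both arms, and section 7.2 plans no between-arm analysis of serious events.

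Finally, the case report form (Attachment 6) and the adverse event forms (Attachment 7) are not part of the text reviewed. They may capture more than 8.2 requires. If so, the protocol text should say so.

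**Conclusion.** The point holds in a limited form. Following the plan as written does not secure an all-cause serious-event count by arm, because the only classification covering hospitalisation, disability and death is filtered by a causal judgement and 8.2 records device effects only. This rests on reading A of the list and on the forms not going beyond 8.2.

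The direction of any distortion depends on facts the plan omits. If the judgement is masked, events are removed from both arms by opinion. Section 8.5 says the team expects no adverse events directly due to rtACS, which may tilt that opinion towards unlinked. If allocation is known, sham events can hardly qualify. The size cannot be fixed from the documents; under the assumed 30% attribution, 70% of serious events go unclassified.

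No planned test or efficacy result is affected. The gain from correcting this is unbiased descriptive safety data for the study's own monitoring and for the larger trial. The change should be made because a stated rule, and not merely missing detail, excludes the events, and the repair is cheap.

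**What to change.** 1. In 8.1, define a serious adverse event by outcome alone, in either arm: any one of criteria 2 to 6, with the wording on rtACS as the cause removed from criteria 5 and 6. Use *serious* throughout, and set out the list so that its logic is unambiguous.
2. Keep events related to rtACS as a subset, identified by the separate relatedness item.
3. Extend the 8.2 recording rule, including the seriousness and relatedness items, to all adverse events.
4. State who judges relatedness, and that it is judged before any unmasking.
5. In section 7.2, add a descriptive table of serious events by arm, first from all causes and then by relatedness.

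Deleting criterion 1 alone would not be enough. It would leave a category headed as related to rtACS with no general relatedness test, and 8.2 would still be limited to device effects.

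The cost is wording in 8.1, 8.2 and 7.2 and an instruction on the case report form. The downside is slightly more recording, and a few unrelated events in the serious-event table.

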8.2 Recording of Adverse Device Effects

Prior to and at each contact with the participant, the investigator will evaluate adverse device effects by examination and, as appropriate, by specific questioning. Information on all adverse device effects will be recorded immediately in the source document and in the appropriate adverse effect module of the Research Activities Checklist (see Attachment 7) and Case Report Form. All clearly related signs, symptoms, and abnormal diagnostic procedure results will be recorded in the source document, grouped under one diagnosis.

All adverse device effects occurring during the study period will be recorded. The clinical course of each event will be followed until resolution, stabilization, or until it has been determined that the study treatment or participation is not the cause. Serious adverse device effects that are still ongoing at the end of the study period will be followed up to determine the final outcome (see section 8.3).

The minimum initial information to be captured in the participant's source document concerning the adverse device effect includes:

- Study identifier
- Study Center
- Subject number
- Device model and serial number
- A description of the event
- Date of onset
- Investigator assessment of the association between the event and study treatment
- Current status
- Whether study treatment was discontinued
- Whether the event is serious and reason for classification as serious

8.3 Reporting of Adverse Device Effects and Unanticipated Problems

8.3.1 Investigator Reporting: Notifying the IRB

Federal regulations require timely reporting by investigators to their local IRB of unanticipated problems posing risks to participants or others. The following describes the NYULMC IRB reporting requirements, though investigators at participating sites are responsible for meeting the specific requirements of their IRB of record.

Report promptly, but no later than 5 working days:

Researchers will submit reports of the following problems promptly but no later than 10 working days from the time the investigator becomes aware of the event:

- ***Unanticipated problems including adverse events that are unexpected and related***
 - *Unexpected: An event is “unexpected” when its specificity and severity are not accurately reflected in the protocol-related documents, such as the IRB-approved research protocol, any applicable investigator brochure, and the current IRB-approved informed consent document and other relevant sources of information, such as product labeling.*
 - *Related to the research procedures: An event is related to the research procedures if in the opinion of the PI, the event was more likely than not to be caused by the research procedures.*
 - *Harmful: either caused harm to participants or others, or placed them at increased risk*
- ***Unanticipated adverse device effect:*** Any serious adverse effect on health or safety or any life-threatening problem or death caused by, or associated with, a device, if that effect, problem, or death was not previously identified in nature, severity, or degree of incidence in the investigational plan or application (including a supplementary plan or application, or any other unanticipated serious problem associated with a device that relates to the rights, safety, or welfare of subjects).

CONFIDENTIAL

This material is the property of the NYU School of Medicine and Langone Medical Center. Do not disclose or use except as authorized in writing by the study sponsor

Other Reportable events:

The following events will be promptly reported to the IRB, though no later than 10 working days:

- **Complaint of a research subject** when the complaint indicates unexpected risks or the complaint cannot be resolved by the research team.
- **Protocol deviations or violations** (includes intentional and accidental/unintentional deviations from the IRB approved protocol) for any of the following situations:
 - *one or more participants were placed at increased risk of harm*
 - *the event has the potential to occur again*
 - *the deviation was necessary to protect a subject from immediate harm*
- **Breach of confidentiality**
- **Incarceration of a participant** when the research was not previously approved under Subpart C and the investigator believes it is in the best interest of the subject to remain on the study.
- **New Information indicating a change to the risks or potential benefits** of the research, in terms of severity or frequency (e.g., analysis indicates lower-than-expected response rate or a more severe or frequent side effect, other research finds arm of study has no therapeutic value, FDA labeling change or withdrawal from market).

Reporting Process

The reportable events noted above will be reported to the IRB using the Reportable Events Log (see Attachment 7) or as a written report of the event (including a description of the event with information regarding its fulfillment of the above criteria, follow-up/resolution and need for revision to consent form and/or other study documentation).

Copies of each report and documentation of IRB notification and receipt will be kept in the Regulatory Binder.

